#### 8.10 Long term follow-up assessments

Randomised participants who have completed the treatment phase of the trial (visits 2-8) will be required to attend a 3-month follow-up visit (visit 9, 90 to 97 days after visit 2), and a 6-month follow-up visit (visit 10, 180-187 days after visit 2); there will also be an optional 12-month follow-up online assessment (see section 8.10.1). Table 2 (page 46) outlines which assessments will be carried out at visits 9 and 10.

#### 8.10.1 Opportunistic 12-month follow-up

We will collect opportunistic data at 12 months (360 days + 7days) post randomisation from participants recruited to the trial in years 1 and 2, to assess long-term effects of KARE therapy on alcohol use, social functioning and mental health. At their 6-month follow-up visit (visit 10), participants will be advised that they will have the opportunity to complete the 12-month online assessment and advised to keep drink diaries until this point. A link to the online assessment will be emailed to

participants 360 days after randomisation for completion. Participants will have been asked to provide optional informed consent for data storage for the purposes of the trial at baseline. Data will be collected on number of days of heavy drinking via TLFB and drink diaries, as well as social functioning (SF-36) and mental health (BDI, change in WHO risk levels).

The site team will call participants prior to the 12-month follow-up window to remind those participants who consented to take part in the opportunistic follow-up about the email link they will receive and reconfirm their email address. If participants are happy to complete the questionnaires they will be emailed a link to provide follow-up data.

#### 8.11 Qualitative assessments

Participants will be invited to take part in an optional qualitative component of the trial. An open-ended survey will be provided to those participants who opt-in to the qualitative aspect of the trial at visit 1 asking about preconceptions around ketamine. Those participants will then be invited to take part in semi-structured interviews over the phone concerning their experiences with the intervention following the final data collection point (6 months/visit 10). They will have 3 months (90 days) to participate.

Data will be analysed using reflexive thematic analysis [62], around 30 participants are likely to be required to reach saturation. Three or four participants will be identified from each site, following asking them at randomisation whether they wish to take part.

#### 8.12 Withdrawal criteria

Participants who withdraw before Visit 2 (Baseline) will be replaced by assigning successive screening IDs to eligible participants, but after completing eligibility checks and breathalyser on visit 2, participants will be randomised and will not be replaced.

Participants have the right to withdraw at any time and there is no obligation to provide reasons for withdrawal. Participants who discontinue any aspect of the trial treatment, would still be invited to complete the follow-up visits at 3 months (visit 9) and 6 months (visit 10), unless they fully withdraw from the trial. A participant cannot choose to discontinue one element of the treatment package, i.e. if they discontinue from IMP treatment they cannot continue with therapy/education or vice versa. Participants wishing to withdraw their consent from the trial should contact a member of their site trial team to make

their wishes known. In addition, the CI and/or PI may discontinue a participant from the trial at any time it is considered necessary for any reason including:

- Ineligibility (either arising during the trial or retrospectively)
- Significant non-compliance with treatment or trial requirements e.g. If the participant misses 2 consecutive infusions, as detailed in section 9.11
- An adverse event which requires discontinuation of the trial medication or results in inability to continue to comply with trial procedures
- Disease progression which requires discontinuation of the trial medication or results in inability to comply with trial procedures
- Consent withdrawn, loss of capacity or detention under Mental Health Act
- Pregnancy, see section 10.6.
- In the case of an overdose with ketamine, the participant will be withdrawn from the trial (see section 10.7)
- Positive urine screen for ketamine after randomisation. Participants would be withdrawn from treatment but invited to continue to 3-month and 6-month follow-up.

However, all efforts will be made to maintain participants in the trial where possible and to continue assessments as intended. If treatment is stopped for longer than 7 days in this trial, then it will not be possible to resume treatment. The reason for participant withdrawal will be recorded in the withdrawal/change in participation eCRF and medical notes (or source data file if no medical notes are available) within 24 hours of the site trial team becoming aware.

Where the participant has/is withdrawn due to an AE, the investigator or delegate should follow the procedures documented in section 10.3 in order to assess the safety of the IMP. It should be made clear to any participant specifically withdrawing consent for further data collection that data already collected will be retained for analysis, and data pertaining to safety will continue to be collected for regulatory reporting purposes and will be included in any safety analysis and the final analysis. Furthermore, if any significant new information becomes available in regard to the treatment they have received in the trial it may be necessary to contact them in the future about this.

If a participant becomes uncontactable and stops engaging with the trial they will be deemed 'lost to follow-up'. Every effort will be made to attempt to continue collecting full protocol assessments from

REDACTED Version 8.0, 18/JUN/2024; IRAS ID: 1008179 MORE-KARE protocol those lost to follow-up and/or participants who repeatedly deviate from the protocol. Our PPI team suggested one phone call and a follow up email / letter would be appropriate. All protocol deviations and violations will be recorded and reported to the Sponsor.

All participants who withdraw, or who are lost to follow-up, will still have the option to receive information about the trial, including newsletters and end of trial results unless they opt not to receive them.

The trial may be stopped before completion for the following reasons:

- If the CI and/or Sponsor decide to suspend the trial pending safety review of an emergent issue
- The CI and /or Sponsor decide to stop the trial for safety, administrative or other reasons

All available data from participants who change their participation status following randomisation will be included in the analyses as appropriate.

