. We included four groups in this proof-of-concept study: 1) ketamine+psychological therapy (*KARE therapy*); 2) ketamine+ alcohol education (AlcEd); 3) placebo+psychological therapy, 4) placebo+AlcEd, to identify whether treatment effects were improved by adding KARE therapy alongside ketamine. Our AlcEd condition was a placebo for the psychological therapy, 7 sessions delivered at the same time points/intervals as psychological therapy was, which matched the time spent with the therapist but included no active psychological intervention.

For the primary outcome of percentage of days abstinent from alcohol at six months' follow-up, the greatest abstinence rate was observed in the KARE therapy arm (*active/active*), then ketamine+AlcEd (active/control), then placebo+psychological therapy (control/active), with lowest abstinence seen in the placebo+AlcEd arm (control/control) (see Figure 1).

We now need to take this work forward to provide definitive evidence of the efficacy of KARE therapy as a treatment for AUD, to inform a step change in treatment of AUD in the UK.

In this trial, rather than using saline placebo, we now propose including a very low, sub-therapeutic dose of ketamine to control for the functional unblinding that can occur with ketamine administration [44] by better controlling expectancy, as participants will be told they will receive one of two doses of ketamine. We have found this approach to be effective at better preserving the blind in a previous RCT [45]. Our PPI group also felt that this change may improve retention still further (which was 20% attrition at six months in proof-of-concept study) as participants would be told they would be receiving one of two doses of the study drug.

Ketamine is now established as a rapid acting anti-depressant [44] and esketamine (an enantiomer of the drug) is licensed for use in treatment-resistant depression [46]. Depressive symptoms are rife in alcohol use, particularly following detoxification [47]. Conventional anti-depressants are at best only mildly effective in alcoholism [34], which is problematic as depressive symptoms precipitate relapse [48-50]. Treating depressive symptoms during the vulnerable period post-detoxification may be one mechanism through which ketamine and combined therapy is an effective treatment in AUD.

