Timeline Follow Back		x	х	X h		Х		Х		Х	Х	Х	Х
Drink Diary										Х	х	Х	х
Fagerstrom Nicotine Dependence				Xi						х	Х	Х	
SADQ		Х	Х								Х	Х	

REDACTED Version 8.0, 18/JUN/2024; IRAS ID: 1008179

Page 48 of 105

	Pre- Screening (telephone)	Screenin g	Refresher Screening	Baseline		Treatment Phase					Follow Up			
Visit #	-1	1	1	2	3	4	5	6	7	8	9 F-UP	10 F-UP	Opportunistic 11 F-UP	
CTQ				Xi										
SF-36				Xi						Х	Х	Х	х	
CGI				Xi						Х	Х	Х		
Hood Mysticism Scale		Х		Xi		Х		Х		Х	Х	х		
Change in WHO risk level		Х		Xi						Х	Х	х	Х	
EQ5D5L				Xi								х		
ICECAP-A				Xi								х		
Expectancy of treatment questionnaire		х												
Treatment guess (BANG blinding index)										х				
3 Things Task				Xi		Х		Х		Х	Х	Х		
APEQ					Х		Х		Х	Х				
BAI				Xi						Х	Х	Х		
Readiness to Change scale		X												

REDACTED Version 8.0, 18/JUN/2024; IRAS ID: 1008179 MORE-KARE protocol

	Pre-	Screenin	Refresher	Baseline Treatment Phase							Follow Up			
	Screening	g	Screening											
	(telephone)													
Visit #	-1	1	1	2	3	4	5	6	7	8	9 F-UP	10 F-UP	Opportunistic 11 F-UP	
	Therapist/re	esearcher		Medic/cli	nician		Researc	h Nurse						

\* In the week prior to Visits 2, 4, 6, 8, 9 and 10 participants will be telephoned to remind them of their attendance.

- a. Physical Height, weight, an examination of cardiovascular, respiratory, GI, GU and neurological function to a level of detail that would be expected for a patient due to receive anaesthesia.
- b. Vital signs: oral/tympanic temperature, resting pulse, pulse oximetry and blood pressure.
- c. Bloods (Screening) FBC (haemoglobin, white cell count, platelets, mean red cell volume); Liver function (Bilirubin, ALT, ALP, AST, Albumin, gamma-glutamyl transpeptidase (GGT)), Biochemistry (urea, sodium, potassium, glucose, calcium, thyroid stimulating hormone).
- d. Bloods (Trial): ketamine; Liver function (Bilirubin, ALT, ALP, AST, Albumin, gamma-glutamyl transpeptidase (GGT)), and platelets.
- e. Urine Drug screen (Screening, infusion days and F-UP visits) (methamphetamine, cocaine, THC, benzodiazepines, amphetamines, morphine, methadone, ketamine).
- f. Urine Drug screen (Non-infusion days in the treatment phase) (methamphetamine, cocaine, THC, benzodiazepines, amphetamines, morphine, methadone,).
- g. BACtrack app installed on visit 1/visit 2 checked and data recorded on subsequent visits
- h. Pre-randomisation assessments during the baseline visit (visit 2)

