- The alcohol TimeLine Follow Back (TLFB) is a drinking assessment method that obtains estimates of daily drinking and has been evaluated with clinical and nonclinical populations. Using a calendar, people provide retrospective estimates of their daily drinking over a specified time period. Several memory aids can be used to enhance recall (e.g., calendar; key dates serve as anchors for reporting drinking; standard drink conversion). The alcohol TLFB has been shown to have good psychometric characteristics with a variety of drinker groups, and can generate variables that provide a wide range of information about an individual's drinking (e.g., pattern, variability, and magnitude of drinking).
- Participants will be given access to a drink diary to use at home in between Visits 8, 9 and 10.
   Participants will be asked to record their alcohol consumption every day in between trial visits.
   Drink diaries are regularly used in alcohol research to record subjective alcohol consumption.
- Alcohol Craving Questionnaire short-form (ACQ-NOW) is a 12-item scale that assesses current alcohol craving.
- Montgomery-Asberg Depression Rating Scale (MADRS) is a clinical interview used in patients with suspected depression and rates patients on a variety of depression related scales.
- Alcohol Abstinence Self Efficacy Scale is a 20-item self-report questionnaire which evaluates a person's potential to abstain from drinking alcohol.
- Snaith-Hamilton Pleasure Scale (SHAPS) is a questionnaire used to assess the presence of anhedonia.
- Ketamine side-effect scale (KSET) is a questionnaire that assesses acute and longer-term side effects associated with ketamine treatments.
- Clinician-Administered Dissociative States Scale (CADSS) is a structured clinical interview to assess state dissociation rated by clinicians.
- SADQ- Severity of Alcohol Dependence Scale assesses current severity of alcohol dependence.
- World Health Organisation alcohol use disorders inventory categorises risk level of current drinking.
- EQ-5D-5L- assesses health-related quality of life.
- ICECAP-A assesses wellbeing and capability in adults for economic evaluation.
- Stanford Expectancy of treatment questionnaire [64] assesses patient expectancy of treatment outcome in clinical trials.

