# 9.12 Assessment of compliance with treatment

Compliance includes adherence to both to IMP and protocol trial procedures. The trial medication will be administered by the research medic/nurse only in the context of the participant attending the trial site facility. Participants will not be responsible for any trial medication. A member of the site team will ensure that the arrangements for each treatment visit are agreed with the participant. Where necessary, the site team will assist in transportation. If a participant fails to attend a clinic visit for the infusion then the site team will endeavour to contact the participant to identify the reason. Where possible an alternative appointment will be made within the infusion visit window (see Table 2 page 46). If the participant fails to attend a clinic visit for the follow-up day the site team will endeavour to contact the participant to identify the reason and where possible arrange an alternative visit within the follow-up visit window (see Table 2 page 46). All episodes of failure to attend visits will be recorded in the medical notes, eCRF and protocol deviation log (eCRF). If the participant misses 2 consecutive infusions, then they will be withdrawn from treatment and will be invited to attend follow up visits 9 and 10 as part of our intention to treat protocol. Non-compliance to the protocol trial procedures will be documented by the site team and reported to ExeCTU via the eCRF. Persistent non-compliance (attendance <80% for treatment visits i.e. visits 2-8) may lead the participant to be withdrawn from the trial.

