- Reasons for exclusions listed on site screening logs to assess whether language barriers are present and if any appropriate improvements to the trial can be made.

**Mechanistic study:** For the mechanistic study, we will collect depression symptom data (MADRS) and examine relationships with drinking outcomes using mediation analysis based on structural equation modelling.

Moderated mediation analyses will be performed using PROCESS version 3.5 [72] using Model 8, bootstrapping set to 5000 samples and with confidence intervals of 95%. In these analyses, the predictor variable (X) will be the Intervention Condition **and the outcome** (Y) variable will be days of heavy drinking at 6 months follow-up. The moderator (W) will be the family history of alcohol use disorder (Positive vs Negative) which has emerged from recent work in depression as predictive of better treatment outcome (e.g. [73, 74], see [75] for a review) and our own exploratory analyses from the proof of concept trial (see UPLOADS; Morgan et al., in prep). The mediators will be respectively the depressive symptoms as indexed using standard self-report and clinician rated symptom scales (BDI and MADRS) as well as the aggregated indicator from our natural language processing analyses at the post-treatment follow-up in three separate moderated mediation analyses.

We will also use the Automated Social Identity assessment (ASIA), a freely available pattern classifier tool we have developed that relies on computational linguistics and uses a binary classification model to determine which identities are salient in a person at a particular moment. ASIA has been trained to identify 'depressed' natural language to 85% accuracy [53, 76].

We will aggregate and analyse natural linguistic data for each treatment week (weeks 1 to 4), and then aggregate responses monthly until the 6-month period (months 2, 3, 4, 5, 6). We will calculate the probability of being 'depressed' or 'recovered' in each group and use latent growth curve modelling to examine whether trajectories differ with regards to these groups. We will then use Cox regression models to examine whether ASIA identity probabilities are predictive of relapse.

The mechanistic insights from these analyses would be whether:

- 1. Changes in alcohol use disorder are mediated by earlier changes in depression and anxiety which in turn suggests:

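### Participants who stop treatment are invited only to visits 9 and 10, so the sole treatment guess and the end-of-treatment BDI, MADRS and BAI, all at visit 8, would miss early stoppers

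*Protocol*

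**What the plan says.** Section 8.12 states that participants who discontinue treatment "would still be invited to complete the follow-up visits at 3 months (visit 9) and 6 months (visit 10", unless they withdraw from the trial altogether. The two treatment components stop together: "if they discontinue from IMP treatment they cannot continue with therapy/education or vice versa". Section 9.12 repeats the rule for two consecutive missed infusions: "will be invited to attend follow up visits 9 and 10 as part of our intention to treat protocol". Section 10.7 does the same after an overdose. Section 8.10 counts visits 2 to 8 as the treatment phase, and Table 2 marks a therapy or education session at visit 8.

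Table 2 marks the row "Treatment guess (BANG blinding index") at visit 8 only. BDI, MADRS and BAI are marked at baseline and then at visits 8, 9 and 10, so visit 8 is their only end-of-treatment measurement.

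Two planned uses depend on these data. Section 2 explains that the very low ketamine dose replaces saline "to control for the functional unblinding that can occur with ketamine administration". Section 4.2.1 hypothesises that mood and anxiety at the end of treatment predict later heavy drinking, and section 11.3.7 takes the mediators "at the post-treatment follow-up in three separate moderated mediation analyses".

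Section 8.12 also contains a general aim to keep participants in the trial and carry on with the planned assessments. It does not say how this fits with an invitation that names only visits 9 and 10.

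**The concern.** The primary analysis follows participants whether or not they stay on treatment (11.3.3). Two supporting analyses rely on a visit that stoppers are not asked to attend.

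**Blinding.** The comparator dose was chosen to protect the blind, and the treatment guess is the direct check on it. Section 9.7 withdraws from treatment anyone with intolerable side effects. They may be among those with the clearest idea of their dose, yet no guess would be sought from them. The index would then describe only those who reached visit 8.

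**Mediation.** BDI and MADRS are two of the three named mediators, and BAI serves the anxiety part of the hypothesis. Under 8.9.1, a participant who attends highly intoxicated and then misses the rearranged visit is withdrawn from treatment. Some early relapsers would therefore have an outcome but no end-of-treatment mood score, so the loss is plausibly related to the outcome.

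A statistical analysis plan can decide how to handle missing values. It cannot recover a guess or a score that was never sought.

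**Working it through.** The plan states no figure on this point, so the check sets the visit schedule against the invitation rule.

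1. **Visit windows (Table 2).** Visit 4 is 4 to 21 days after visit 2, visit 6 is 4 to 21 days after visit 4, and visit 8 is 4 to 14 days after visit 6.
   - Earliest visit 8: 4 + 4 + 4 = day 12 after visit 2.
   - Latest visit 8: 21 + 21 + 14 = day 56.
   - Visit 8 has no other anchor. Without a visit 6 it has no defined date.

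2. **Who is left out.** A participant who stops before visit 6 has neither an invitation nor a window. One who stops after visit 6 has a window but still no invitation.

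3. **What is lost.** The treatment guess is lost completely, because no other visit schedules it. For BDI, MADRS and BAI only the end-of-treatment value is lost. The next value is at visit 9 (days 90 to 97), which is 90 − 56 = 34 to 97 − 12 = 85 days after visit 8. By then about half of the 180-day outcome window has passed. A visit 9 score therefore cannot show what section 11.3.7 wants to show, that mood changed before drinking did.

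4. **Possible repair by analysis.** The imputation in 11.3.4 is for the primary outcome and continuous outcomes at 6 months. It does not mention mediators at visit 8.

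5. **Number affected.** No discontinuation rate is given, so a range is assumed. Participants without these data = 280 × proportion stopping before visit 8:
   - 5%: 280 × 0.05 = 14
   - 10%: 280 × 0.10 = 28
   - 20%: 280 × 0.20 = 56

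6. **Side check on drinking recall.** TLFB is taken at visits 2, 4, 6, 8, 9 and 10. The days that visit 9 must cover depend on the last earlier TLFB:
   - visit 2: 90 to 97
   - visit 4: 90 − 21 = 69 to 97 − 4 = 93
   - visit 6: 90 − 42 = 48 to 97 − 8 = 89
   - visit 8: 34 to 85

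   Everyone who attended visit 9 then recalls 180 − 97 = 83 to 187 − 90 = 97 days at visit 10.

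**The case against.** The strongest reply is that no section forbids visit 8 assessments for stoppers. Section 8.12 aims to continue planned assessments, and also seeks full assessments from those lost to follow-up or repeatedly deviating. This reduces the point to an inconsistency for some stoppers, but does not remove it. A site needs a window to book the visit, and early stoppers have none. The specific instruction in 9.12, "they will be withdrawn from treatment and will be invited to attend follow up visits 9 and 10", is the one that staff would act on.

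It can also be said that the mechanistic outcome is exploratory, that the blinding index is not a listed endpoint, and that limited contact may help to keep stoppers for the primary outcome. These points are fair, and they limit the weight of the finding. A guess given after one infusion is also not equivalent to one given after three, which is why separate reporting is needed.

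A reader might infer more than the documents support:
- **That early TLFB exists only in completers.** It is collected at visits 4 and 6 until the participant stops, and it is retrospective, so visit 9 can reach back. Recall is longer for early stoppers, but recall of 83 to 97 days is routine for all at visit 10. TLFB is also cross-referenced with breathalyser and transdermal data.
- **That the diary is denied to stoppers.** Section 8.9.1 says "Participants will be given access to a drink diary to use at home in between Visits 8, 9 and 10", and Table 2 also marks it at visits 9 and 10. When stoppers would receive it is unclear, not excluded.
- **That visit 8 contains completers only.** Someone who misses one infusion can still reach it.
- **That all three mediators are lost.** The 3 Things Task, the source of the language mediator, is also done at visits 2, 4, 6, 9 and 10.
- **That the mediation analysis is restricted to completers.** The protocol does not specify a complete-case analysis.

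**Conclusion.** The point holds in a limited form. As written, the protocol seeks no treatment guess and no end-of-treatment BDI, MADRS or BAI from participants who stop before visit 8. Those who stop before visit 6 have no window in which these could be taken. The blinding index and the end-of-treatment mood mediators would then describe a selected group, while the primary analysis includes stoppers who return for follow-up.

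The range of 14 to 56 of 280 rests wholly on the assumed 5% to 20%. The 20% in sections 2 and 11.2 is phase II attrition, not treatment discontinuation, and should not be read as a forecast of this number. The documents also do not show that stopping differs by dose or that stoppers guess better, so neither the direction nor the size of any bias in the blinding index can be given. The primary outcome is not undermined. This is a cheap improvement to data collection and needs to be made before the participants concerned pass the window.

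**What to change.** In sections 8.12, 9.12 and 10.7, invite participants who have stopped treatment to the visit 8 assessments as well as to visits 9 and 10. Specify:

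- **Content:** assessments only, with no infusion and no therapy or education session. Collect the treatment guess, BDI, MADRS, BAI and TLFB, and issue the drink diary at this contact so that its timing is clear.
- **Timing:** a window counted from visit 2 that matches when completers reach visit 8, days 12 to 56. Add it as a note to Table 2.
- **Mode:** by telephone where possible. The participant may decline.
- **Reporting:** the Bang index for all randomised participants who gave a guess, and separately for those who completed treatment, with the number lacking a guess in each treatment group.

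The rules on when treatment stops are unchanged. The instruments are already scheduled for every participant, so the cost is a short amendment and one extra contact for people who have stopped.
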